2.2.2 Clinical Adverse Event Profile

Anticipated adverse events (AEs) or adverse device effects (ADEs) associated with use of this device include, 1) injury to the patient subject (patient in ABCD) or user subject (healthcare provider), 2) patient subject claustrophobia. 3) patient subject anxiety, 4) difficulty performing intubation with or without requiring removal of the device. Serious adverse events (SAEs) or serious adverse device effects (SADEs) would include 1) major injury to the patient or provider. Unanticipated adverse device events (UADEs) would include device breakdown. Based on the pre-clinical simulations (intubation and CPR), there is a low risk of increased technical difficulty during intubation and the device remains firmly in place during chest compressions for CPR. There is minimal anticipated risk, as noted above, to the user subject or patient subject. The device will remain on a patient for the duration of an aerosol generating procedure and then for a defined period post-procedure to simulate aerosol evacuation.

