2.3.3 Assessment of Potential Risks and Benefits

The study subjects for this trial of a biocontainment device for aerosol generating procedures are frontline healthcare workers. The device is placed on top of a patient. The closest equivalent to this device is a face shield worn by a healthcare worker, which would provide no added significant risk to a patient for any procedure. This secondary “face shield” is placed over the patient as an added layer of protection during high risk procedures for generation of aerosols. Based on the results in Section 2 above, the preclinical risks of the device interfering with intubation, the most high-risk aerosol-generating procedure under investigation in this study, are small, but potentially could be serious if they occurred. **The primary goal of this study is to assess use of the device for planned airway procedures involving general anesthesia to better assess the feasibility for using this device as part of aerosol-generating procedure protocols for patients with highly transmissible (airborne or droplet) infectious diseases (i.e. COVID-19).** The benefits of this device are adding an additional layer of PPE protection for high risk aerosol generating procedures that has the potential to reduce risk of contracting COVID-19. There is also a potential benefit of containment of infectious aerosols to reduce contamination of surfaces and equipment in rooms where aerosol generating procedures are performed which may help streamline patient care, workflow and sanitation procedures long-term.

Risk of injury to a study subject or patient from this device is minimal. The device is lightweight, sturdy with good optical clarity for performing aerosol generating procedures. Below is a breakdown of major risk/failure points and steps taken to mitigate and assess risk by topic.

Environment:

1. *Site or sub-site location for device use.* There is a future risk of non-uniform device use due to cultural and environmental differences among units and hospitals where the device will be used. The initial study will involve two sites that are in close physical proximity, work closely together and are part of the same health system (HUP and PPMC) which will help inform appropriate changes to the label/user manual for device use.

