1. *Supply Chain:* Failure to secure a reliable supply chain for disposable elements of the device could result in inability to use device to fullest capacity and reduce effectiveness of protection against droplet and aerosol. Goal is to ensure reliable inventory of disposable components by keeping accurate logs of device use and remaining supplies, have an accurate estimate of need and burn rate for supplies and give manufacturing partner(s) adequate lead time for all components to be produced, shipped, and deployed in a timely fashion.

Methods:

1. *Device availability:* Each site/sub-site that is part of the study will have a designated storage location for units and associated disposable equipment. Given the restrictions on non-clinical staff in the hospital at this time, research coordinators/team members will not be onsite to bring equipment from storage to the room. The study PIs or subIs or study users will bring the device and associated components to the room for the procedure.
2. *Inability to perform intubation:* There is a small risk of inability to perform intubation with this device. The device has been designed to optimize hand positioning and mobility to triangulate the hands toward the patient's airway. The device safety straps have a quickly release function to rapidly remove the device and proceed with intubation if needed in the event the user has difficulty performing an intubation with the device in place.

Equipment:

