Patient-subjects will be recruited from among the patients assigned to a recruited anesthesiologist's case-load. Given the constraints and timing of these assignments, the patient-subjects will need to be recruited on the day of the procedure. Patients will be approached by a study investigator or designee and asked about willingness to participate in study testing a new droplet and aerosol containment device for the anesthesia airway portion of the procedure. They will be informed that use of the device will not affect or influence their medical care. No specific gender, age, race, or ethnicity criteria will be used in the recruitment of subjects. The goal is to recruit 150 patients over weeks 1-6 of the study. We anticipate full recruitment during this time. Patient participation after completion of the study intervention in the operating room will be in the form of a survey with the goal for survey completion within 1-week of the intervention. Patients will be recruited solely on a voluntary basis with the option to withdraw at any time from the study without any form of penalty. This study is voluntary and no compensation or additional incentives will be provided.

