8.3.2 Classification of an Adverse Event

8.3.2.1 Severity of Event

Adverse events will be classified based on the defined grading system:

- Mild: events require minimal or no treatment and do not interfere with the participant's daily activities
- Moderate: events result in low level of inconvenience or cause some inference with functioning
- Severe: events interrupt a participant's usual daily activity. Severe events are usually potentially life-threatening or incapacitating. Please note, the term "severe" does not necessarily equate to "serious".

8.3.2.2 *Relationship to Study Intervention*

All adverse events (AEs) and ADEs must have their relationship to the study device assessed by the PI who examines and evaluates the participant based on temporal relationship and his/her clinical judgment. The degree of certainty about causality will be graded using the categories below. In a clinical trial, the study product must always be considered.

- Definitely Related – The AE/ADE is known to occur with the device.
- Probably Related – There is a reasonable possibility that the device caused the AE, or there is a temporal relationship between the device use and event. Reasonable possibility means that there is evidence to suggest a causal relationship between the device and the AE/ADE.
- Possibly Related - There is a possibility that the device caused the AE, or there is a temporal relationship between the device use and event. There is no evidence to suggest a causal relationship between the device and the AE/ADE but an alternate etiology has not yet been established.
- Unrelated – There is not a reasonable possibility that the use of the device caused the event, there is no temporal relationship between the use of the device and event onset, or an alternate etiology has been established.

8.3.2.3 *Expectedness*

Expected adverse events associated with this study that will be tracked and reported include:

1. Minor injury to the patient subject or provider
2. Patient claustrophobia
3. Patient anxiety
4. Difficulty performing intubation with the device in place
5. Need to remove the biocontainment device to safely perform intubation

Potential SAEs associated with this study would include:

1. Major physical injury to patient or provider due to device failure.

A UADE for this device would be breakdown or malfunction of the device during use.

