9 STATISTICAL CONSIDERATIONS

9.1 *Statistical Hypotheses*

We hypothesize that the biocontainment device will be a safe and effective option for performing airway procedures in patients while also providing additional protection during an aerosol generating procedure.

Primary Efficacy Endpoints:

1. We hypothesize that the time to perform an airway procedure with the biocontainment device will be equivalent to time for airway procedure without the biocontainment device. Alternatively, there will be prolonged airway procedures times with the device. This endpoint will be analyzed every two weeks.
2. We anticipate that the number of AEs or ADEs will be low and will also decrease over time. This endpoint will be analyzed on a weekly basis.

Secondary Efficacy Endpoints:

1. We hypothesize that the median Likert ratings for User subject device comfort will be weighted toward “strongly agree”. Alternatively, we will see ratings favoring “neutral” or “disagree” for user subject device comfort.
2. We hypothesize that the median Likert ratings for User subject additional healthcare burden comfort will be weighted toward “strongly disagree”. Alternatively, we will see ratings favoring “neutral” or “agree” on increased healthcare burden.
3. The median Likert ratings for the Patient Experience survey will be weighted toward minimal patient discomfort or anxiety. Alternatively, we will see ratings favoring increased patient discomfort or anxiety inside the device.
3. We anticipate that the median Likert ratings of the patient experience post-survey will indicate overall good user comfort and low levels of anxiety or claustrophobia in the device.

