10.1.1.2 Consent Procedures and Documentation

Informed consent is a process that is initiated prior to the individual's agreeing to participate in the study and continues throughout the individual's study participation. Consent forms will be Institutional Review Board (IRB)-approved and the participant will be asked to read and review the document. The investigator will explain the research study to the participant and answer any questions that may arise. A verbal explanation will be provided in terms suited to the participant's comprehension of the purposes, procedures, and potential risks of the study and of their rights as research participants. Participants will have the opportunity to carefully review the written consent form and ask questions prior to signing. The participants should have the opportunity to

discuss the study with their family or surrogates or think about it prior to agreeing to participate. The participant will sign the informed consent document prior to any procedures being done specifically for the study. Participants must be informed that participation is voluntary and that they may withdraw from the study at any time, without prejudice. A copy of the informed consent document will be given to the participants for their records. The informed consent process will be conducted and documented in the source document (including the date), and the form signed, before the participant undergoes any study-specific procedures. The rights and welfare of the participants will be protected by emphasizing to them that the quality of their medical care will not be adversely affected if they decline to participate in this study.

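### Section 5.5 has patients told that the device makes no difference to their care, an assurance that the plan's own risk sections do not support and that prejudges the question under test

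*Combined protocol and SAP*

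**What the plan says.** Section 5.5 (Patient Subject Recruitment and Retention) has patients approached on the day of the procedure by an investigator or designee. They are asked about a new containment device for the airway part of their anesthetic, and then: "They will be informed that use of the device will not affect or influence their medical care". No qualification follows.

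Other sections describe what the device may do:

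- Section 2.2.2 includes among anticipated events "difficulty performing intubation with or without requiring removal of the device", together with injury, claustrophobia and anxiety.
- Section 2.3.3 says that the risks of interference with intubation "are small, but potentially could be serious if they occurred", and later: "There is a small risk of inability to perform intubation with this device".
- Section 8.3.2.3 includes among the expected events to be tracked "Need to remove the biocontainment device to safely perform intubation".
- Section 9.1 hypothesizes that airway procedure time "will be equivalent to time for airway procedure without the biocontainment device", and continues: "Alternatively, there will be prolonged airway procedures times with the device".

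On consent, Section 10.1.1.1 calls for forms that set out the risks in detail. Section 10.1.1.2 calls for a verbal explanation of potential risks before signing, and its own assurance is that "the quality of their medical care will not be adversely affected if they decline to participate in this study".

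**The concern.** Staff who follow Section 5.5 as written give patients an unconditional statement about a device that, according to the synopsis, has never been used in a healthcare setting. The same plan lists ways in which the device could alter the airway procedure and makes two of them, procedure time and adverse events, its primary endpoints.

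What is at stake is the accuracy of what patients hear when deciding, on the day of their procedure, whether to take part. They would hear that the device makes no difference to their care and, in the consent discussion, that it carries risks to their airway management. A patient cannot tell which message to rely on.

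**Working it through.** The point rests on a comparison of texts. The plan gives no figure on it, so there is none to reproduce.

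**1. What the sentence covers.** Its subject is use of the device, not participation. The sentence before it concerns the airway part of the anesthetic, so airway management is the care most directly in view. Nothing limits the assurance to the underlying operation or to treatment decisions.

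**2. Against the listed risks.**

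- Difficult intubation, with or without removal of the device: anticipated in 2.2.2 and expected in 8.3.2.3.
- Inability to intubate with the device in place: a small risk in 2.3.3.
- Interference with intubation: small in probability, potentially serious (2.3.3).
- Minor injury, claustrophobia, anxiety: 2.2.2, 2.3.1, 2.3.3 and 8.3.2.3.
- Time in the device after the procedure: 2.2.2 and 6.1.2 both keep it in place for a period.

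Each of these, if it occurs, affects the patient's care. The supporting evidence on intubation in 2.2 is preclinical and simulated.

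**3. Against the hypothesis.** Section 9.1 hypothesizes equivalent times, with prolonged times as the alternative. The synopsis expects times only to approach those without the device. The assurance therefore agrees with the hypothesis and conflicts with the alternative: it announces one answer before the trial has tested it.

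**4. Against the plan's other assurances.** Earlier in 5.5, healthcare workers are assured that volunteering, declining or withdrawing has no bearing on employment or access to protective equipment. Section 10.1.1.2 assures patients about declining. Both concern the decision to participate. Only the patient sentence in 5.5 attaches the assurance to the device.

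**5. Reach.** Section 1.3 plans 150 procedures, 100 with the device and 50 without. Section 9.2 screens at least 175 patients. All who are approached are to hear the sentence, and 100 are then to undergo the procedure in the device.

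**6. Could an unqualified assurance hold for 100 patients?** The documents give no rate of events that affect care, so the rates here are assumptions. With rate p per patient and independent patients, the chance of at least one event is 1 − (1 − p)^100:

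- p = 0.5%: 39%
- p = 1%: 63%
- p = 2%: 87%
- p = 5%: 99%

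Even a trial with no such event in 100 device patients would leave an upper 95% limit of 1 − 0.05^(1/100) = 3.0% (one-sided) or 1 − 0.025^(1/100) = 3.6% (two-sided). A fully reassuring result would still not establish that the device has no effect on care. These figures are illustrative; the inconsistency stands without them.

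**The case against.** The strongest reply is that patients are properly informed elsewhere. Sections 10.1.1.1 and 10.1.1.2 require a detailed written account of risks, a verbal explanation, and time for questions and reflection, all before signing. This stands. A reader might infer that patients consent on an inaccurate statement; the documents do not support that, because full disclosure is also required. What remains is that the plan directs staff to say two things that do not agree.

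A second reply is that the sentence means only that clinical decisions are unchanged. Section 2.2.1 says that the device does not interact with drugs or affect airflow, 6.2.4 leaves airway technique to the attending anesthesiologist, 2.3.1 provides for removal of the device, and 5.2 excludes known or anticipated difficult airways. That may be what was intended, but the text does not say so. Nor does a small or minimal risk amount to no effect.

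Three further inferences are tempting and should not be drawn:

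- *That the sentence contradicts the hypothesis.* The hypothesis is safety and equivalence, with which the sentence agrees. It conflicts only with the stated alternative.
- *That 5.5 and 10.1.1.2 contradict each other.* One concerns device use and the other concerns declining, so both could be said. The second is narrower and is the one the plan can support.
- *That the assurance biases the patient survey.* Patients in the device arm rate perceived safety, anxiety and comfort (8.1), so priming is possible. But only that arm is surveyed, so no comparison between arms is distorted, and neither the presence nor the size of an effect can be derived.

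**Conclusion.** The sentence in Section 5.5 is wrong as written, at modest severity. It gives every patient approached an assurance that does not fit the risks in 2.2.2, 2.3 and 8.3.2.3, and it presumes the answer to the question in 9.1. The consequence is inconsistent messages to 150 planned patients, mitigated by the disclosure that 10.1.1.1 and 10.1.1.2 require. No endpoint definition, sample size or analysis is affected.

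The conclusion assumes that staff would follow 5.5 literally and that patients would count airway management as part of their care. It does not depend on the wording of the consent form, which is not available here.

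**What to change.** Replace the sentence in Section 5.5 with text that does three things:

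- assures patients that declining or withdrawing will not affect their care, in line with 10.1.1.2;
- states that use of the device carries the risks already listed in 2.2.2, 2.3 and 8.3.2.3;
- says that whether the device prolongs the airway procedure is what the study tests (9.1).

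Any recruitment text in use should be brought into line with this and with the consent form. The cost is a short protocol edit. The downside is that a few more patients may decline.

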6 STUDY INTERVENTION

6.1 Study Intervention(s) Administration

6.1.1 *Study Intervention Description*

The intervention consists of a biocontainment and aerosol clearance device that will be tested in the controlled setting to assess feasibility to perform airway procedures under general anesthesia with the device. There is no specific control device for this product. The control condition for this intervention will consist of airway procedures per routine clinical protocols without the biocontainment device. This study will be performed initially in locations where a patient would undergo a scheduled airway procedure under general anesthesia on non-COVID-19 patients. All participants in this study as well as non-participants who are present in the room during the airway procedure (aerosol-generating procedure) will continue to use appropriate level of PPE per hospital protocols and policies. This device does not replace standard aerosol-protecting PPE. The device likely falls into a class II device classification with the closest FDA-approved device consisting of a face shield. This device will be used as part of an abbreviated IDE as there is minimal risk to the subject as well as minimal risk to a patient during use of the device by a study subject (see **risk/benefit assessment Section 2.3** above). The device is not commercially available and is being used as part of this study.

The dimensions of the device are 23 inches (Width) x 20.5 inches (Height) x 13.5 inches (Depth). The frame is composed of aluminum with clear polycarbonate sides and top. The front of the box has two hand ports and one instrument port. The sides of the box have one hand port each. The top has a single suction port for aerosol evacuation. Hand and instrument port covers are multilayered vinyl and self-sealing. Suction tubing for

simulation of aerosol evacuation consists of standard suction tubing (Conmed tubing $\frac{1}{4}$ inch inner diameter) and the sheeting to cover the upper torso/close off the distal end of the device consists of a disposable, clear plastic sheet. This is a new device without a specific model number. Validation studies for this device are described in [Section 2.2](#) above.

6.1.2 Dosing and Administration

The biocontainment device is designed to fit over the head and neck of a person and should accommodate shoulder width up to 23 inches (average biacromial distance in the United States is 14.1 inches for women and 16.1 inches for men). The portion of the device over the torso has a drop-down sheet that will fit over all patients regardless of body habitus and will function to contain droplet and aerosol. The biocontainment device has functionality to remove aerosol during and after a procedure. The device is designed to utilize the wall suction system, assuming wall suction at 70 L/min (rate at HUP – 100 L/min). The device is currently undergoing additional laboratory testing to assess aerosol containment and evacuation. The device will be connected to wall suction during this trial. Standard $\frac{1}{4}$ inch inner diameter suction tubing currently utilized in the hospital is attached to the suction port on the top of the device by an assistant or primary proceduralist. The suction tubing is connected to the wall suction. For the purposes of this trial on COVID-19 negative patients, this will represent an active suction process with aerosol evacuation which, in theory, would remain on for the duration of the procedure and the device and suction remain in place for 11 minutes post-procedure to ensure evacuation of 99.9% of aerosols (See [Figure 2 in Section 2 above](#)).

6.2 Preparation/Handling/Storage/Accountability

6.2.1 Acquisition and accountability

The biocontainment devices will be manufactured and shipped to the study sponsor. Devices will be distributed to designated storage areas in participating study site as designated by the site PIs/subIs. All devices will have a unique identification number for tracking of device location and use. Cleaning and storage of devices will be performed as described in the protocol ([See Section 6.2.4 below](#)). At the completion of the study, all devices will be cleaned as per the study protocol, placed in plastic/storage bags and stored by the sponsor in a designated locked, clean room prior to handling by other team members. Following evaluation of the devices by the PIs or their designees as well as the engineering team, the devices will be stored for an additional 3 months in a locked, clean room. When the entire study is deemed complete, the devices will be disposed of as biohazardous waste.

